9.5 SAS, AIMS, and BARS

Change from baseline in SAS, AIMS, and BARS scales for trial visits during the open-label treatment phase using the Safety Sample will be summarized by descriptive statistics. In addition, incidence of BARS Global Clinical Assessment of Akathisia during the open-label treatment phase by severity category will be provided. Descriptive statistics will be summarized at each visit using the OC data set and at the last visit (Week 12/ET) using the LOCF data set.

9.6 Suicidality Data

Suicidality will also be monitored during the study using the C-SSRS [CC1] [REDACTED] and will be summarized as number and percentage of subjects reporting any suicidal behavior, ideation, behavior by type (4 types), ideation by type (5 types) and treatment emergent suicidal behavior and ideation. Summary will be provided for the open-label treatment phase.

Suicidality is defined as report of at least one occurrence of any type of suicidal ideation or at least one occurrence of any type of suicidal behavior during assessment period (count each person only once).

Treatment emergent suicidal behavior and ideation is summarized by four types: Emergence of suicidal ideation, Emergence of serious suicidal ideation, Worsening of suicidal ideation, Emergence of suicidal behavior.

Emergence of suicidal behavior/ideation is defined as report of any type of suicidal behavior/ideation during treatment when there was no baseline suicidal behavior/ideation.

Emergence of serious suicidal ideation is defined as observation of suicidal ideation severity rating of 4 or 5 during treatment when there was no baseline suicidal ideation.

Worsening of suicidal ideation is defined as a suicidal ideation severity rating that is more severe than it was at baseline.

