5.2.2 Exclusion Criteria

Subjects will be excluded if they meet any of the following exclusion criteria at the time points described in the schedule of assessments (Table 1.3-1).

Sex and Reproductive Status

- 1) Sexually active males or females of childbearing potential (FOCBP) who do not agree to practice 2 different methods of birth control or remain abstinent during the trial and for 30 days after the last dose of IMP. If employing birth control, 2 of the following precautions must be used: vasectomy, tubal ligation, intrauterine device, birth control pill, birth control implant, birth control depot injection, condom with spermicide, sponge with spermicide, or occlusive cap (vaginal diaphragm or cervical/vault cap) with spermicide.
Consensual sexual activity that cannot biologically result in pregnancy may not be subject to required birth control methods, following discussion with the medical monitor.
Male subjects must also agree not to donate sperm from trial screening/baseline through 30 days after the last dose of IMP.
- 2) Women who are breastfeeding and/or who have a positive pregnancy test result prior to receiving IMP.

Medical History and Concurrent Disease

3) Subjects who fulfill the following criteria related to suicide and/or suicidal ideation at entry are excluded:

- Subjects who have a significant risk of committing violent acts, serious self-harm, or suicide, or those who are homicidal or considered to be a high risk to others, or subjects with a response of “yes” on the Columbia-Suicide Severity Rating Scale (C-SSRS) Suicidal Ideation Item 5 (Active Suicidal Ideation with Specific Plan and Intent), OR
- Subjects with a response of “yes” on the C-SSRS Suicidal Behavior Items Actual Attempt, Interrupted Attempt, or Aborted Attempt
- Subjects who endorse engaging in preparatory acts and/or non-suicidal self-injury may be included according to investigator judgment, provided the behavior has not increased significantly in frequency or severity during the preceding double-blind trial period, and after discussion and approval by the medical monitor.

Note that subjects with a response of “yes” on the C-SSRS Suicidal Ideation Item 4 (Active Suicidal Ideation with Some Intent to Act, without Specific Plan and Intent) may be included following discussion with the medical monitor.

Physical and Laboratory Results

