7.1 Baseline Definition

Baseline is defined as the last available measurement prior to the first dose of open-label IMP in the open-label treatment phase.

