- CT-3.2.1 Medical History (Enrolled Sample)
- CT-3.2.2 Psychiatric History (Enrolled Sample)
- CT-3.2.3 Borderline Personality Disorder Disease History (Enrolled Sample)
- CT-3.3 Baseline Psychiatric Scale Evaluation (Enrolled Sample)
- CT-4.1.1 Concomitant Medications: Medications Taken Prior to Start of Study Therapy (Safety Sample)
- CT-4.1.2 Concomitant Medications: Medications Taken During Study Therapy Period (Safety Sample)
- CT-4.1.3 Concomitant Medications: Medications Taken Post Study Therapy Period (Safety Sample)
- CT-4.2.1 Psychiatric Concomitant Medications: Medications Taken Prior to Start of Study Therapy (Safety Sample)
- CT-4.2.2 Psychiatric Concomitant Medications: Medications Taken During Study Therapy Period (Safety Sample)
- CT-4.2.3 Psychiatric Concomitant Medications: Medications Taken Post Study Therapy (Safety Sample)

CCI

CCI

- CT-6.1 Summary of Mean Change from Baseline in Simpson-Angus Scale (SAS) Total Score (Safety Sample)
- CT-6.2 Summary of Mean Change from Baseline in Abnormal Involuntary Movement Scale (AIMS) Total Score and Item Scores 8, 9 and 10 (Safety Sample)
- CT-6.3.1 Summary of Mean Change from Baseline in Barnes Akathisia Rating Scale (BARS) Global Clinical Assessment of Akathisia (Safety Sample)
- CT-6.3.2 Incidence of Barnes Akathisia Rating Scale (BARS) Global Clinical Assessment of Akathisia (Safety Sample)
- CT-6.4.1 Columbia-Suicide Severity Rating Scale(C-SSRS), Suicidality (Safety Sample)
- CT-6.4.2 Columbia-Suicide Severity Rating Scale(C-SSRS), Suicidal Behavior by Type (Safety Sample)
- CT-6.4.3 Columbia-Suicide Severity Rating Scale(C-SSRS), Suicidal Ideation by Type (Safety Sample)
- CT-6.4.4 Columbia-Suicide Severity Rating Scale(C-SSRS), Treatment Emergent Suicidal Behavior and Ideation (Safety Sample)
- CT-6.4.5 Columbia-Suicide Severity Rating Scale (C-SSRS) – Listing of Treatment Emergent Suicidal Ideation (Safety Sample)
- CT-6.4.6 Columbia-Suicide Severity Rating Scale (C-SSRS) – Listing of Treatment Emergent Suicidal Behavior (Safety Sample)
- CT-6.4.7 Columbia-Suicide Severity Rating Scale (C-SSRS) – Listing of Treatment Emergent Serious Suicidal Ideation (Safety Sample)
- CT-6.4.8 Columbia-Suicide Severity Rating Scale (C-SSRS) – Listing of Worsening Suicidal Ideation (Safety Sample)
- CT-7.1 Extent of Exposure to Study Medication (Safety Sample)
- CT-7.2 Number and Percentage of Subjects Receiving Study Medication and Mean and Range of Average Daily Dose (Safety Sample)

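### A suicide attempt on treatment is not counted as treatment-emergent suicidal behaviour when the baseline C-SSRS already records preparatory acts

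*SAP*

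**What the plan says.** **Treatment-emergent types.** SAP 9.6 gives four: "Emergence of suicidal ideation, Emergence of serious suicidal ideation, Worsening of suicidal ideation, Emergence of suicidal behavior". Three concern ideation and one concerns behaviour.

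**Emergence.** The condition is "report of any type of suicidal behavior/ideation during treatment when there was no baseline suicidal behavior/ideation".

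**Worsening.** This exists for ideation only: "Worsening of suicidal ideation is defined as a suicidal ideation severity rating that is more severe than it was at baseline". The table list in SAP 12 matches. CT-6.4.6 lists treatment-emergent behaviour and CT-6.4.8 lists worsening ideation; no output is planned for worsening behaviour.

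**Behaviour types.** SAP 9.6 also plans summaries of "behavior by type (4 types), ideation by type (5 types"), but never names the four behaviour types.

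**Entry.** Protocol 5.2.2, criterion 3, excludes a positive answer on the "C-SSRS Suicidal Behavior Items Actual Attempt, Interrupted Attempt, or Aborted Attempt". It then adds: "Subjects who endorse engaging in preparatory acts and/or non-suicidal self-injury may be included according to investigator judgment". That allowance has two conditions: the behaviour must not have increased significantly during the double-blind trial, and the medical monitor must approve.

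**Baseline.** SAP 7.1: "Baseline is defined as the last available measurement prior to the first dose of open-label IMP in the open-label treatment phase". Protocol 8.7.5 and SAP 10.2.12 specify the Since Last Visit form of the C-SSRS at every visit.

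**The concern.** The protocol admits some subjects who already have one kind of suicidal behaviour at baseline. The only treatment-emergent category for behaviour requires that there be none. Escalation from a preparatory act to an attempt is then neither emergence (behaviour was present at baseline) nor worsening (defined for ideation only).

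CT-6.4.4 is the one planned C-SSRS table that sets on-treatment findings against baseline. Suicidal ideation and behaviour on the C-SSRS are a secondary safety endpoint, and Protocol 2 describes patients with this disorder as prone to self-harm, including suicide. A reader who takes the behaviour row of CT-6.4.4 as the number of subjects with new suicidal behaviour on drug would miss this escalation.

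The rule also departs from the SAP's own approach elsewhere. Under SAP 9.1, an adverse event continuing from baseline becomes treatment-emergent if it worsens or turns serious. SAP 9.6 applies that idea to ideation but not to behaviour.

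**Working it through.** The plan has no figure to reproduce, so the check applies the SAP 9.6 definitions as logical rules.

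**Step 1: are preparatory acts a behaviour type?** SAP 9.6 counts four types. Criterion 3 names three kinds of attempt, plus preparatory acts and non-suicidal self-injury. The last is by its name not suicidal, so preparatory acts are taken as the fourth type. This is an inference.

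**Step 2: the subject.** Baseline: preparatory acts recorded, no attempt. On treatment: an actual, interrupted or aborted attempt.

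**Step 3: admissible ideation ratings.** Criterion 3 excludes a positive answer on ideation item 5 and allows item 4 after discussion with the medical monitor. Baseline ideation *b* therefore runs from 0 (none) to 4, and on-treatment ideation *t* from 0 to 5. That gives 5 × 6 = 30 combinations.

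**Step 4: the rules.** The slash in the emergence definition can be read term by term (behaviour against baseline behaviour, ideation against baseline ideation) or jointly (neither present at baseline).

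- Emergence of behaviour: behaviour on treatment and none at baseline; the joint reading also requires *b* = 0.
- Emergence of ideation: *t* > 0 and *b* = 0; the joint reading also requires no baseline behaviour.
- Emergence of serious ideation: *t* ≥ 4 and *b* = 0.
- Worsening of ideation: *t* > *b*.

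**Step 5: results for a subject with an attempt on treatment.**

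| Baseline behaviour | Reading of the slash | Emergent behaviour | In any of the four types | In none |
|---|---|---|---|---|
| Preparatory acts | Term by term | 0 of 30 | 15 of 30 | 15 of 30 |
| Preparatory acts | Joint | 0 of 30 | 15 of 30 | 15 of 30 |
| None | Term by term | 30 of 30 | 30 of 30 | 0 of 30 |
| None | Joint | 6 of 30 | 16 of 30 | 14 of 30 |

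In the first two rows, the 15 come from *t* > *b*: 5 + 4 + 3 + 2 + 1 = 15 for *b* = 0 to 4. Those subjects appear only in an ideation row. These are counts of logical combinations, not probabilities.

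The last row shows why the slash matters. On the joint reading, an attempt by a subject with no baseline behaviour but some baseline ideation is also not counted as emergent behaviour.

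**Step 6: with an attempt row.** If the rule is an attempt on treatment with no attempt at baseline, neither ideation nor preparatory acts enter it, and all 30 of 30 combinations are counted.

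**The case against.** The strongest reply is that the attempt is already visible. CT-6.4.1 and CT-6.4.2 cover all on-treatment suicidality and behaviour by type. Criterion 3 bars attempts at entry and Protocol 5.2 allows no eligibility exceptions, so, eligibility deviations aside, every attempt in CT-6.4.2 is new relative to baseline. An attempt recorded as an adverse event with onset on or after the first dose is a TEAE under SAP 9.1 and, if serious, appears in CT-8.5.1 and listing CT-9.2. The trial is open-label and descriptive, and no test or decision depends on CT-6.4.4.

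Most of this stands. A reader might infer that the attempt disappears from the report, or that it is not treatment-emergent in any output. The documents do not support that: the event is misclassified in one table and one listing.

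Two things remain. First, CT-6.4.4 and CT-6.4.6 carry the treatment-emergent label and would be incomplete under it, while CT-6.4.2 by its title reports by type and does not promise one count of subjects with any attempt. Second, the adverse event route is partial: Protocol 8.8.2 restricts reporting of exacerbations to those with unusual, severe or unexpected features, so aborted or interrupted attempts are less certain to be recorded.

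A reader might also infer that every subject admitted with preparatory acts is affected. That goes too far. Only acts captured at the baseline assessment count. Acts reported only at earlier double-blind visits leave baseline behaviour negative, and a later attempt would then count as emergent on the term-by-term reading.

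**Conclusion.** The gap is real and follows from the stated rules on either reading of the slash. If preparatory acts are recorded at baseline, no rule in SAP 9.6 counts a later attempt as treatment-emergent suicidal behaviour. The effect is an incomplete behaviour row in CT-6.4.4 and an incomplete listing CT-6.4.6; for these subjects the error can only be an undercount.

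The conclusion rests on two conditions: preparatory acts are the fourth behaviour type (inferred), and they fall in the last Since Last Visit assessment before the first open-label dose.

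It is tempting to state what share of attempts would be missed. The documents do not support any figure: they give no proportion entering with preparatory acts, no attempt risk and no sample size, so any percentage would reflect only the inputs chosen. The number of subjects could be none. Nor is the endpoint as a whole shown to be biased, since the protocol says only that ideation and behaviour will be assessed with the C-SSRS and leaves the detail to the SAP. This is a modest correction, worth making because the table is the one meant to show change from baseline.

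**What to change.** In SAP 9.6 and SAP 12:

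1. Add a row to CT-6.4.4, emergence of suicide attempt: any actual, interrupted or aborted attempt during treatment when none of these was present at baseline, each subject counted once.
2. Extend listing CT-6.4.6 to the same subjects.
3. Name the four behaviour types.
4. State that the emergence definition is read term by term: behaviour against baseline behaviour, ideation against baseline ideation.

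A ranked worsening-of-behaviour row is optional. It needs an ordering of the behaviour types, which the documents do not give, and the attempt row closes the gap without one. The entry criteria need no change.

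The cost is SAP wording, one table row and a wider listing, all from data already collected. Treatment-emergent counts may be slightly higher, and the new row will partly overlap the attempt rows of CT-6.4.2.

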9.7 Concomitant Medications

Number and proportion of patients taking concomitant medications prior to the open-label treatment phase, during the open-label treatment phase, and after study therapy are tabulated by drug classification using the WHO drug dictionary

9.8 Extent of Exposure

The start date of the open-label study therapy - brexpiprazole - will be the first day of dosing during the open-label treatment phase. The number and percentage of patients who receive study medication during the open-label treatment phase, will be presented by week. Each dosing week will be based on the actual week; i.e., Day 1-7 in Week 1, Day 8-14 in Week 2, etc. This summary will be performed on the Safety Sample.

The mean daily dosage will be summarized by week using descriptive statistics. The mean daily dosage per patient per week will be determined for each week of the study. This will be calculated by dividing the sum of individual total doses by the number of days in the week interval. The summary will contain the number of patients receiving study medication during the open-label treatment phase, and the mean and range of the mean daily dose for each week.

10 Conventions

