6.1 Trial Treatments Administered

The first dose of open-label brexpiprazole will be taken one day after the last dose of double-blind IMP is taken for the previous double-blind, brexpiprazole BPD trial so that treatment continues without interruption. It is anticipated that the last dose of IMP of the double-blind trial will be taken the day of the treatment last visit of the previous double-blind brexpiprazole BPD trial (ie, the day of the screening/baseline visit for the open-label trial). If a subject is unable to rollover immediately, up to 3 days may be permitted between the end of the double-blind trial and the start of IMP in the open-label extension trial; however, this must be discussed with the medical monitor.

All subjects will receive a starting dose of 1 mg/day at the screening/baseline visit, followed by an increase to 2 mg/day at the end of Week 1 (Table 6.1-1). Subjects may increase their dose to 3 mg/day at the investigator's discretion on or after the Week 2 visit, depending on treatment response and tolerability. Subjects taking 3 mg/day may down-titrate to 2 mg/day based on tolerability at any time during the course of the trial. Subjects unable to tolerate 2 mg/day will be discontinued from the trial. Dose adjustments to brexpiprazole must be made in increments of 1 mg/day. Dose decreases

for brexpiprazole can occur at unscheduled visits and dose increases for brexpiprazole can only occur at scheduled visits.

As applicable, dose changes of background antidepressant therapy (ADT) can be modified to achieve optimum efficacy and tolerability. Dose adjustments of ADT should not occur at the same visit as a dose adjustment of brexpiprazole and a recommended minimum of 5 days should occur between any dose adjustments of brexpiprazole or ADT at any point during the trial.

Table 6.1-1 Dosing Schedule			
IMP	Screening/Baseline - Week 1	Week 1 - Week 2	Week 2 - Week 12^a
Brexipiprazole	1 mg/day	2 mg/day	2 or 3 mg/day ^b

^aDown titration can occur at any time due to tolerability after Week 2. The minimum dose allowed is 2 mg/day.

^bOption to titrate to 2 or 3 mg/day (ie, 2 mg, or 3 mg) based on clinical response and tolerability; changes must occur in 1 mg/day increments.

For information regarding the dose regimen and treatment period(s), including any follow-up period(s), see [Section 4.1](#).

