Due to COVID-19, delayed entry subjects are permitted to be screened for Trial 331-201-00195 up to 90 days after completing the last scheduled treatment visit of the previous double-blind BPD trial (discussion with the medical monitor is required if > 90 days have passed). These subjects will be screened for eligibility at a separate screening visit for Trial 331-201-00195, where they will undergo full assessments to determine eligibility. The screening period will be up to 21 days and may be extended upon discussion with the medical monitor. The delayed entry subjects will also undergo a separate baseline visit, and the assessments from that visit will serve as the baseline measures for Trial 331-201-00195. Delayed entry subjects will receive the first dose of IMP at the baseline visit.

Treatment Phase: Eligible subjects will receive daily treatment with open-label brexpiprazole beginning at the screening/baseline visit. Visits will occur at the end of Weeks 2, 4, 8, and 12. Telephone contact will be made at Weeks 1, 6, and 10 to assess adverse events (AEs) and concomitant therapy. In addition, an optional telephone call or other form of communication will be made with the subject approximately 1 week (\pm 2 days) after the visit (e.g., at Weeks 3, 5, 7, 9, and 11) to check on status. All subjects will receive up to 12 weeks of open-label treatment in this trial.

Follow-up: Subjects will be followed for safety via telephone contact or clinic visit 21 (\pm 3) days after the last dose of open-label brexpiprazole.

See [Figure 3.1-1](#) for a schematic of the trial design.

^aThe last visit of the previous double-blind BPD trial will serve as the baseline measures for Trial 331-201-00195. If a subject is unable to rollover immediately, up to 3 days may be permitted between the end of the double-blind trial and the start of IMP in the open-label extension trial; however, this must be discussed with the medical monitor.

^bTelephone contact or clinic visit.

^cTelephone contact will be made at Weeks 1, 6, and 10 to assess AEs and concomitant therapy.

Figure 3.1-1 Trial Design Schematic

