3.2 Trial Treatments

The first dose of open-label brexpiprazole will be taken one day after the last dose of double-blind IMP is taken for the previous double-blind, brexpiprazole BPD trial so that treatment continues without interruption. It is anticipated that the last dose of IMP of the double-blind trial will be taken the day of the treatment last visit of the previous double-blind brexpiprazole BPD trial (i.e., the day of the screening/baseline visit for the open-label trial). If a subject is unable to rollover immediately, up to 3 days may be permitted between the end of the double-blind trial and the start of IMP in the open-label extension trial; however, this must be discussed with the medical monitor. Delayed entry subjects will receive the first dose of IMP at the baseline visit. All subjects will receive a starting dose of 1 mg/day at the screening/baseline visit, followed by an increase to 2 mg/day at the end of Week 1 (Table 3.2-1). Subjects may increase their dose to 3 mg/day at the investigator's discretion on or after the Week 2 visit, depending on treatment response and tolerability. Subjects taking 3 mg/day may down-titrate to 2 mg/day based on tolerability at any time during the course of the trial. Subjects unable to tolerate 2 mg/day will be discontinued from the trial. Dose adjustments to brexpiprazole must be made in increments of 1 mg/day. Dose decreases for brexpiprazole can occur at unscheduled visits and dose increases for brexpiprazole can only occur at scheduled visits.

As applicable, dose changes of background antidepressant therapy (ADT) can be modified to achieve optimum efficacy and tolerability. Dose adjustments of ADT should not occur at the same visit as a dose adjustment of brexpiprazole and a recommended minimum of 5 days should occur between any dose adjustments of brexpiprazole or ADT at any point during the trial.

Table 3.2-1 Dosing Schedule			
IMP	Screening/Baseline - Week 1	Week 1 - Week 2	Week 2 - Week 12 ^a
Brexipiprazole	1 mg/day	2 mg/day	2 or 3 mg/day ^b

^aDown titration can occur at any time due to tolerability after Week 2. The minimum dose allowed is 2 mg/day.

^bOption to titrate to 2 or 3 mg/day (i.e., 2 mg, or 3 mg) based on clinical response and tolerability; changes must occur in 1 mg/day increments.

4 Sample Size and Power Justification

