10.1 Study Visit Windows

Study visit windows will be used to map visits using study day intervals. Observations at each scheduled visit and Early Termination will be assigned to Week 2, Week 4, Week 8 and Week 12 visits based on their visit windows as shown in [Table 10.1A](#). This visit window convention applies to tables and listings for all efficacy and safety scales (CC1 [REDACTED])

CCI

SAS, AIMS and BARS). This derived study window variable will be named as DAY and will be footnoted. In listings, it will be listed along with the CRF study visit.

Table 10.1A shows classifications for study day intervals in the open-label treatment phase. The variable “target day” is defined using the number of days since the start of open-label brexpiprazole dosing. The first day of open-label brexpiprazole dosing is defined as “Day 1”.

If more than one observation falls within a particular study day interval, then the last observation within that interval is used. Evaluations occurring more than 7 days after the last open-label brexpiprazole dosing date will not be mapped into study visit windows, and will be excluded from the analysis.

Table 10.1A: Study Day and Visit Windows in the Open-label Treatment Phase

Week	Target Day ^a	Study Day Interval ^a
2	14	2-21
4	28	22-42
8	56	43-70
12	84	71-91 ^b

^a Relative to the first day of open-label brexpiprazole in the open-label treatment phase.

^b Evaluations occurring more than seven days after the last dosing date of open-label brexpiprazole in the open-label treatment phase will be excluded from the efficacy analyses.

[figure not shown]

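### SAP 9.8 has no denominator rule for the week in which dosing ends, so the weekly mean daily dose is understated in that week

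*SAP*

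**What the plan says.** SAP 9.8 (Extent of Exposure) fixes the weeks by study day: "Each dosing week will be based on the actual week; i.e., Day 1-7 in Week 1, Day 8-14 in Week 2, etc". Each subject's mean daily dose for a week comes from "dividing the sum of individual total doses by the number of days in the week interval". The summary, listed as CT-7.2, gives for each week the number of patients receiving medication and "the mean and range of the mean daily dose for each week".

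The doses against which that table will be read are in SAP 3.2 and Protocol 6.1. On the start of treatment, where the step up is set for the close of Week 1: "All subjects will receive a starting dose of 1 mg/day at the screening/baseline visit, followed by an increase to 2 mg/day at the end of" […]. On the upper dose: "Subjects may increase their dose to 3 mg/day at the investigator's discretion on or after the Week 2 visit". For the period from Week 2 to Week 12, footnote a of Protocol Table 6.1-1 adds: "The minimum dose allowed is 2 mg/day". On duration, SAP 3.1 says: "All subjects will receive up to 12 weeks of open-label treatment in this trial".

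Nothing in SAP 9.8 shortens the interval when dosing ends inside it, and nothing says how dosing after Day 84 is displayed. SAP 6.2 does name a treatment end date for subjects lost to follow-up, but for the compliance calculation; 9.8 does not refer to it. The visible statistical section of the protocol (Section 9) has no exposure formula that would fill the gap.

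**The concern.** With fixed 7-day blocks, the literal divisor is 7. A subject who stops on the fourth day of a week has four days of dose divided by seven, and the three days off treatment enter as zeros. The same subject is still counted among those receiving medication that week, so numerator and denominator describe different periods.

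This is not confined to dropouts. Protocol Table 1.3-1 allows ± 3 days around the visits, and SAP Table 10.1A puts the Week 12 target at Day 84. Completers can therefore finish on about Day 81 to 87, and many will have a partial last week or a few days in an extra week.

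In a flexible 2 to 3 mg/day trial whose visible objective is safety and tolerability, CT-7.2 supplies the dose context. A fall in mean dose in the last weeks, with range minima under 2 mg/day, would look like reduced dosing late in treatment when it may only reflect where dosing stopped. One early stopper is enough to set the minimum for a week.

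**Working it through.** The plan gives no exposure figure to reproduce, so the check applies the stated rule to the scheduled visit days.

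**Inputs from the documents**
- Week *w* covers Day 7(*w* − 1) + 1 to Day 7*w* (SAP 9.8). Week 12 is Day 78 to 84; the next block is Day 85 to 91.
- Day 1 is the first open-label dose and the Week 12 target is Day 84 (SAP 10.1).
- The visit window is ± 3 days (Protocol Table 1.3-1), so the Week 12 visit falls on Day 81 to 87.
- Doses after Week 2 are 2 or 3 mg/day (Protocol Table 6.1-1).

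**Assumptions not in the documents:** full compliance, a constant dose, and the last dose on the day of the visit.

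**Formula as written:** weekly mean = dosed days in the week × dose ÷ 7.

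**Week 12 (Day 78 to 84)**

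| Last dose | Dosed days | 2 mg/day | 3 mg/day |
|---|---|---|---|
| Day 81 | 4 | 1.14 | 1.71 |
| Day 82 | 5 | 1.43 | 2.14 |
| Day 83 | 6 | 1.71 | 2.57 |
| Day 84 to 87 | 7 | 2.00 | 3.00 |

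**Week 12 group mean**
- Last-dose days spread evenly over Day 81 to 87: dosed days are 4 + 5 + 6 + 7 + 7 + 7 + 7 = 43 out of 7 × 7 = 49. The mean is 43/49 × 2 = 1.76 mg if all take 2 mg, 43/49 × 2.5 = 2.19 mg if half take 3 mg, and 43/49 × 3 = 2.63 mg if all take 3 mg. Each is 6/49 = 12% low.
- All stop on Day 84 or later: 0% low.
- All stop on Day 81: 1 − 4/7 = 43% low.

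**Block after Week 12 (Day 85 to 91)**

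| Last dose | Dosed days | 2 mg/day | 3 mg/day |
|---|---|---|---|
| Day 85 | 1 | 0.29 | 0.43 |
| Day 86 | 2 | 0.57 | 0.86 |
| Day 87 | 3 | 0.86 | 1.29 |

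With an even spread over these three days the mean is 6/21 × 2 = 0.57 mg, or 6/21 × 3 = 0.86 mg, against 2 or 3 mg taken on each dosed day.

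**Early stops.** The same happens in any week. One dosed day at 2 mg gives 2/7 = 0.29 mg; one dose of 1 mg in Week 1 gives 1/7 = 0.14 mg. In Week 12, a stop on Day 78, 79 or 80 gives 0.29, 0.57 or 0.86 mg at 2 mg/day.

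**Sensitivity.** If the last dose is taken the day before the visit, last-dose days become Day 80 to 86, and a Day 80 stop at 2 mg/day gives 3/7 × 2 = 0.86 mg in Week 12.

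**With the denominator ended at the last dose date**, a compliant subject on 2 mg/day shows 2.00 and one on 3 mg/day shows 3.00 in every partial week.

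**The case against.** **The SAP does not address this case.** It never says that seven days is the divisor when dosing ends mid-week, and a programmer might shorten the interval unprompted. True, but seven is what the wording gives, and a rule that can be programmed two ways yields two different tables. Either way the text needs a sentence.

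**Dose per calendar day is a legitimate measure, and a weekly mean need not equal a prescribed dose.** This stands. A missed dose or a mid-week change between 2 and 3 mg also produces values that nobody was prescribed, so such values alone do not show an error. The difficulty is narrower: off-treatment days are averaged in for a group defined as receiving medication that week.

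**The size rests on an unknown spread.** Also true. The documents give no distribution of last-dose days, no share on 3 mg, and no count of subjects dosed past Day 84. In the even spread, four of the seven last-dose days leave Week 12 complete and unbiased.

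**Stronger readings that the documents do not support.** A reader might infer that Week 12 would show doses below any used in the trial. For in-window completers under the stated assumptions it would not: the lowest value is 1.14 mg, above the 1 mg/day of Week 1. The supportable statement is that Week 12 can fall below the 2 mg/day minimum in the dosing table. A reader might also take this for a miscalculation in the SAP, or for a problem only at the end of the trial. The SAP states no figure that could be miscalculated, and the effect arises in any week in which someone stops.

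**Conclusion.** The point holds as a minor one. As written, SAP 9.8 treats days after the last dose as 0 mg in the subject's final dosing week. CT-7.2 then understates the mean daily dose and distorts the minimum of the range wherever subjects stop.

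For in-window completers the Week 12 mean is between 0% and 43% low, with 12% as the figure for an even spread. Values for the few days after Day 84 are mainly artefact. These sizes depend on full compliance, a constant dose and a last dose on the visit day; subjects who stop earlier in Week 12 would lower the mean further.

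The consequence is descriptive. Adverse event incidence, the primary endpoint, does not use the weekly mean dose, and no inference depends on it.

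**What to change.** Amend SAP 9.8 along these lines:

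- In the week containing the subject's last open-label dose, the denominator is the number of days from the start of that week through the last dose date. Missed doses before that date count as 0 mg.
- All earlier weeks keep a denominator of 7.
- State how days after Day 84 are shown, for example combined with Week 12 under the same denominator rule. A 2 mg/day subject whose last dose is on Day 87 would then show 10 × 2 ÷ 10 = 2.00 mg for Day 78 to 87.

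The denominator should not run from the first to the last dose inside each week, because that would hide missed doses at the edges of a week. A continuing subject who misses the first three days of a week and takes 2 mg on the other four would show 8/4 = 2.00 mg instead of 8/7 = 1.14 mg.

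The cost is a sentence or two in the SAP, a footnote to CT-7.2 and a small change to the program. No new data are needed beyond the dosing dates and doses that the summary already uses.
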